- Parameters of renal function: IP is to be discontinued if the estimated glomerular filtration rate (eGFR) falls to <60 mL/min/1.73m² (calculated using Chronic Kidney Disease Epidemiology Collaboration (CKD-EPI) equation) and where the value is reconfirmed after 24 hrs repeat. Additionally, any subject who requires renal replacement therapy will also have IP discontinued.
- Patient will be immediately discontinued from study drug and followed until resolution of adverse event and laboratory values have returned to baseline, if any of the following criteria occur.
 - a. TB \geq 3.0 mg/dL in individuals with normal baseline TB. In individuals with elevated baseline TB due to known Gilbert's syndrome, doubling of direct bilirubin will prompt immediate discontinuation of the study drug.
 - b. Total CK > 5x ULN
 - c. Amylase and lipase > ULN
 - d. Hemoglobin < 100 g/L or HCT <30%
 - e. Platelets < 100000/ μ L
 - f. WBC <3.5 X 10⁹/L
 - g. if more than 3 patients develop a CTCAE grade 3 or higher in the same category, or if 3 or more patients meet the above individual criteria (a to f) the trial may be stopped and/ or unblinded safety data will be evaluated

Excluded concomitant medications: Patients are not permitted to take thiazolidinedione (pioglitazone, rosiglitazone), chemotherapy, or other investigational medications during the study. Patients should not take any over-the-counter medications or complementary and/or alternative medications without prior consultation of the Investigator.

Permitted concomitant medications: With the exception of excluded concomitant medications, other medications that patients have been taking at stable dosages for at least 3 months before study entry. Statins are permitted as concomitant medications; however, patients will be monitored for statin related toxicity when it is co-administered. Glycemic control medications will be permitted as concomitant medications, including antidiabetic drugs such as metformin, sulfonylureas, dipeptidyl peptidase 4 (DPP-4) inhibitors and insulin. Patients must continue with their current drug regimen without any change in dosage.

Treatment for common illness during the study may be allowed.

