4.4.1 Discontinuation of Subject Investigational Product (IP)

Patients with worsening liver function will not be enrolled in the study. Evidence of worsening liver function will be assessed based on the 2 initial laboratory values used to establish the baseline.

Elevations in ALT and/or AST, occurring after the initiation of study drug, that meet the definition of a potential Case of Drug-Induced Liver Injury per below;

1. If patients with abnormal baseline liver indices develop elevations of AST or ALT greater than 2x baseline or total bilirubin greater than 1.5x baseline values while on study, testing shall be repeated within 48 -72 hours.
2. If there are persistent elevations in ALT or AST greater than 2x baseline or TBL greater than 1.5x baseline values, then close observation (testing and physical examination 2-3 times per week) shall be initiated or study drug will be discontinued
- A decision to discontinue or temporarily interrupt the study drug will be considered based on factors that include how much higher baseline ALT and AST were relative to the upper limit of normal (ULN) and how much the on study ALT and AST levels have increased relative to baseline, in addition to

whether there is concomitant elevation of bilirubin or INR. Study drug will be discontinued or temporarily interrupted:

- a. When the baseline values were < 2x ULN, discontinue if ALT or AST increases to > 5x baseline,
- b. When the baseline values were \geq 2x ULN but < 5x ULN, discontinue if ALT or AST increases to >3x baseline,
- c. When the baseline values were \geq 5x ULN, discontinue if ALT or AST increases to > 2x baseline,
- d. Discontinue if ALT or AST increase > 2x baseline AND the increase is accompanied by a concomitant TBL increase to >2x baseline OR the INR concomitantly increases by >0.2,
- e. In any patients with signs and symptoms of fatigue, nausea, vomiting, right upper quadrant pain or tenderness, fever, rash, and/or eosinophilia (> 5%).

- If a patient lives in a remote area, laboratory testing can be performed locally and the results shall be promptly communicated to the investigator site promptly.
- If patient develops an adverse event of grade 3 that is probably or possibly related to study drug and any patient regardless of attribution to drug who develops a grade 4 or higher Common Terminology Criteria for Adverse Event (CTCAE version 4.03).

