- Parameters of renal function: IP is to be discontinued if the estimated glomerular filtration rate (eGFR) falls to <60 mL/min/1.73m² (calculated using Chronic Kidney Disease Epidemiology Collaboration (CKD-EPI) equation) and where the value is reconfirmed after 24 hrs repeat. Additionally, any subject who requires renal replacement therapy will also have IP discontinued.
- Patient will be immediately discontinued from study drug and followed until resolution of adverse event and laboratory values have returned to baseline, if any of the following criteria occur.

- a. TB \geq 3.0 mg/dL in individuals with normal baseline TB. In individuals with elevated baseline TB due to known Gilbert's syndrome, doubling of direct bilirubin will prompt immediate discontinuation of the study drug.
- b. Total CK $>$ 5x ULN
- c. Amylase and lipase $>$ ULN
- d. Hemoglobin $<$ 100 g/L or HCT $<$ 30%
- e. Platelets $<$ 100000/ μ L
- f. WBC $<$ 3.5 X 10⁹/L
- g. If more than 3 patients develop a CTCAE grade 3 or higher in the same category, or if 3 or more patients meet the above individual criteria (a to f) the trial may be stopped and/or unblended safety data will be evaluated.

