6.2.2 Abnormal Laboratory Findings

In addition, a clinically significant value outside the normal or reference range in a routine safety assessment, such as clinical laboratory, vital signs or ECG, may signify an adverse finding. Additional examinations or repetition of test will be performed as medically indicated.

If the Investigator considers the abnormality as of major relevance, he/she should also record this as an AE. If the findings contribute to a clinical diagnosis (e.g. hepatitis in case of increased liver enzymes), then this diagnosis should be recorded as AE.

The criteria for determining whether an abnormal objective test finding should be reported as an AE are as follows:

1. Test result is associated with accompanying symptoms, and/or
2. Test result requires additional diagnostic testing or medical/surgical intervention, and/or
3. Test result leads to change in study dosing or discontinuation from the study, significant additional concomitant drug treatment or other therapy, and/or
4. Test result leads to any of the outcomes included in the definition of SAE, and/or
5. Test result is considered to be an AE by the Investigator.

For any abnormal test result that meets one of the above conditions except for the last condition, the Investigator will provide a justification for not reporting the abnormal test finding as an AE.

Each AE shall be evaluated for the severity, duration, resolution, action taken and its association with the study treatment. The study participant may be withdrawn or terminated from the study depending on the seriousness of the adverse effects.

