After screening, the eligible patients will be randomly assigned to one of the following treatment groups in addition to their ongoing treatment with UDCA (Patients unable to tolerate UDCA will receive only the investigational medicinal products) i.e., Saroglitzaz magnesium 2 mg, Saroglitzaz magnesium 4 mg, or placebo. Vital signs measurements, weight measurements, physical examination, and laboratory examination will be performed as mentioned in Table 1. Concomitant medications will be recorded. AEs will be noted, if any. Urine pregnancy test will be performed for women of childbearing potential. Subjects will undergo cardiac evaluation (ECG). A 4-week supply of study medication (one bottle) will be dispensed. Baseline quality of life assessment will be performed.

- **Visit 3.1 (Week 2±3 Days)**

Patient will visit study site at 2 weeks after randomization visit for LFTs. The LFTs will be performed at local laboratory.

- **Visit 4 (Week 4±3 Days), Visit 5 (Week 8±3 Days) and Visit 6 (Week 12±3 Days)**

Subjects will be undergo a physical examination and laboratory parameters (safety and efficacy) will be assessed as per Table 1. Vitals signs, body weight will be recorded.

AEs, if any, will be noted. Urine pregnancy test will be performed for women of childbearing potential. Concomitant medications will be recorded. Medication compliance will be checked. Medication will be dispensed on each visit for next 4 weeks.

- **End-of-treatment Visit 7 (Week 16±3 Days)**

Subjects undergo physical examination and laboratory parameters (safety and efficacy) will be assessed as per Table 1. Vitals signs and weight will be recorded. AEs will be noted, if any. Subjects will undergo cardiac (ECG) evaluation. Pregnancy test will be performed for all women of childbearing potential. Concomitant medications will be recorded. Medication compliance will be checked.

- **Safety follow-up Visit 8 End of Study (Week 20±3 Days)**

A safety follow-up visit will be performed 4 weeks after End-of-treatment Visit. Patients clinical examination and safety lab assessment will be performed as per Table 1.

Unscheduled visits- will be allowed any time during the study for assessment and management of AEs and any concurrent clinical conditions. Unscheduled visits shall be captured in the CRF.

- If further investigations are required in case of any AE, Investigator will assess the AE and take necessary action, if required.

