8.3.2 Adverse Events

The applicable definition of an Adverse Event (AE) is in the study protocol. All AEs occurring from when a patient signs informed consent to when a patient exits the study will be accounted for in the reporting. Analysis and presentation of AEs occurring during the screening period will be separated from those occurring during the investigational period where a comparative evaluation of treatment-emergent AEs is intended. A treatment-emergent AE is an event not present prior to exposure to investigational product or any pre-existing event that worsens following exposure to investigational product. The period for treatment-emergent AE analysis starts from the first exposure to the investigational product until the patient exits the study.

Descriptive summaries (frequencies and percentages) for specific AEs will be presented by system organ class and preferred term according to the Medical Dictionary for Regulatory Activities (MedDRA Version 19.1) dictionary by treatment group and overall. In addition to an overall presentation of all AEs, reports will be generated for special classes of AEs such as investigational product related AEs, serious AEs, Maximum severity and AEs resulting in treatment discontinuation by treatment group. These reports will be supported by individual patient listings, as necessary.

Document Title:	Statistical Analysis Plan		
Version Number:	2.0	Date:	11 Nov 2019
Protocol Number:	SARO.16.004	Sponsor Name:	Zydus Discovery DMCC

Adverse events will be counted by the number of events as well as the number of subjects. For the summaries which count the number of patients by treatment group and overall, multiple AEs with the same MedDRA preferred term within the same patient will only be counted once.

Descriptive summaries (frequencies and percentages) for number of subjects experiencing AEs will also be presented.

Only patient listings will be provided for AEs that occur after signing informed consent but prior to exposure to investigational product. These listings will comprise all events occurring during this period in any patient who consented to participate in the study.

These listings will at least contain but not limited to information such as onset and resolution times, maximum severity, causal relationship to study treatment and action taken.

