8.3.5 Laboratory Results

Laboratory values will be presented using the International System of Units (SI units). Clinical laboratory evaluations consist of hematology, clinical biochemistry and urinalysis. Observed and changes from baseline values will be summarized descriptively (N, mean, median, standard deviation, minimum, and maximum values) at each assessment. A summary table of the categorical grade shift changes using the normal ranges from baseline to last study visit will be provided.

For summary purposes, laboratory values that are listed as above or below particular thresholds will be numerically listed as above or below that threshold, respectively, by the minimum measured amount for that parameter. For example, if a parameter is measured to two decimal places, and has a result of “> 6” then, for summary purposes, the value of 6.01

Document Title:	Statistical Analysis Plan		
Version Number:	2.0	Date:	11 Nov 2019
Protocol Number:	SARO.16.004	Sponsor Name:	Zydus Discovery DMCC

will be used. Values with “<” or “>” will be classified as Low or High, respectively, unless such classifications aren’t applicable for that parameter, in which case they will be classified as Normal.

A listing will be provided which contains data for each laboratory parameter. In addition, a listing of all clinically significant abnormal values will be provided.

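### The only categorical laboratory table ends at the last study visit, off drug for completers, and no planned output counts patients per arm against the protocol's own limits

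*SAP*

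**What the plan says.** **Planned laboratory outputs.** SAP 8.3.5 gives descriptive statistics, including the maximum, for values and changes at each assessment. It adds a full listing, a listing of clinically significant abnormal values, and one categorical table: "A summary table of the categorical grade shift changes using the normal ranges from baseline to last study visit will be provided". The section does not define the shift categories. Its rule for results reported with < or > signs sorts them into Low, High or Normal.

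**The last study visit.** Protocol 7.2 places Visit 8 at Week 20 and calls it the end of study: "A safety follow-up visit will be performed 4 weeks after End-of-treatment Visit". Protocol 7.1 says safety laboratory tests are done then.

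**The protocol's limits.** Protocol 4.4.1 sets three ALT/AST tiers by baseline: above 5x baseline if baseline is under 2x ULN, above 3x if it is 2x to under 5x ULN, and, from 5x ULN upward, "discontinue if ALT or AST increases to > 2x baseline". It adds a composite with bilirubin or INR. When these are met, "Study drug will be discontinued or temporarily interrupted". Items a to f are separate limits for bilirubin, CK ("Total CK > 5x ULN"), amylase and lipase, hemoglobin, platelets and white cells. Patients stopped under them are "followed until resolution of adverse event and laboratory values have returned to baseline". There is also a confirmed eGFR limit. Protocol 9.4.4 defines a liver event of clinical interest.

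**Neighbouring outputs.** Protocol 8.3.3 promises frequencies of abnormal laboratory values by arm and visit, without defining abnormal. SAP 8.3.2 tabulates adverse events by arm and names a report on "AEs resulting in treatment discontinuation by treatment group". SAP 2.5 limits the interim to efficacy on liver biochemistries and lipids plus demographic and adverse event summaries, with no subject-level listing.

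**The concern.** A shift from baseline to the last study visit describes where a completer stands about a month after the last dose. A safety reader wants to know how many patients in each arm reached, while on drug, a value that the protocol treats as a reason to stop. The protocol sets no upper limit on ALT or AST at entry and writes a tier for baselines of 5x ULN and above, so some patients may start above ULN. Under a three-level shift they stay High whatever happens in between.

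Safety and tolerability of both doses is a stated objective, and the interim is meant to help choose the phase III dose. A by-arm count against limits that the sponsor has already set is the direct summary for that purpose, and it is not planned.

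**Working it through.** The plan states no figure to reproduce here. SAP 4 says that no formal sample size estimation was done. The check is whether the planned outputs can yield the count. All laboratory values below are assumptions, because the documents give none.

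**Step 1: time off drug at the last visit.** Week 20 − Week 16 = 4 weeks = 28 days. With ±3 days at each nominal week, 28 ± 6 = 22 to 34 days. If Visit 8 is timed from the actual end-of-treatment visit, 28 ± 3 = 25 to 31 days.

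**Step 2: classify assumed patients.** Values are multiples of ULN; above 1 is High. The limit is the multiple in Protocol 4.4.1 times baseline for ALT, and 5x ULN for CK.

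| Patient | Baseline | Peak on drug | Week 20 | Limit | Crossed? | Shift shown |
|---|---|---|---|---|---|---|
| A, ALT | 0.8 | 4.4 | 0.9 | 5 × 0.8 = 4.0 | yes (4.4/0.8 = 5.5) | Normal to Normal |
| B, ALT | 2.0 | 6.2 | 2.0 | 3 × 2.0 = 6.0 | yes (6.2/2.0 = 3.1) | High to High |
| C, CK | 0.7 | 5.5 | 0.9 | 5 | yes | Normal to Normal |
| D, ALT | 1.5 | 1.5 | 1.5 | 5 × 1.5 = 7.5 | no | High to High |
| E, ALT | 1.5 | 7.8 | 7.8 | 5 × 1.5 = 7.5 | yes (7.8/1.5 = 5.2) | High to High |

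A, B and C show the timing problem, which holds for any category scheme if the value has recovered by Week 20. D and E show the size problem: a flat patient and one still above the limit fall in the same cell. That second problem depends on the Low/Normal/High reading.

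**Step 3: one arm.** If A, B and C are in an arm of 12, the true count is 3/12 = 25.0% (exact 95% CI 5.5 to 57.2%). An arm with the same baselines and no crossings has 0/12 (0 to 26.5%). The two shift tables are identical.

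**Step 4: can another output supply the count?**

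| Output | What it shows | What is missing |
|---|---|---|
| By-visit statistics (SAP 6.1, 6.4, 8.3.5) | Largest value and largest change per arm and visit | Number of patients over the limit |
| Abnormal values by arm and visit (Protocol 8.3.3) | On-treatment frequency of abnormal results | Any tie to the limits; a per-patient count across visits |
| Adverse event tables (SAP 8.3.2) | Events by arm, including those leading to discontinuation | A laboratory criterion |
| Final listings (SAP 8.3.5) | Everything needed for a hand count | A table; and not available at the interim |

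A maximum does not convert to a count when baselines differ. A change of +4.2x ULN crosses from baseline 1.0 (5.2 against 5.0) and 2.0 (6.2 against 6.0), but not from 1.5 (5.7 against 7.5) or 2.4 (6.6 against 7.2).

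**The case against.** The strongest reply is that the signal is already visible and only the exact count is absent. Much of that stands.

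- **Interim.** A reader might infer that the interim could hide a crossing behind a falling mean. The documents do not support that. Assume 8 per arm (24/3), all at baseline ALT 2.0x ULN, seven falling to 1.2 and one rising to 6.2. The mean is (7 × 1.2 + 6.2)/8 = 1.825, a fall of 0.175 (8.75%). But SAP 6.1 and 6.4 put the SD (about 1.77), median (1.2) and maximum (6.2) in the same by-visit summary. Against a limit of 6.0, the crossing is in plain view.
- **Adverse events.** Protocol 6.2.2 makes a result reportable when "Test result leads to change in study dosing or discontinuation from the study". That covers temporary interruption as well as stopping. SAP 8.3.2 counts all adverse events by arm and gives its special reports only as examples, so interrupted patients are not lost. Residual gaps remain: 6.2.2 lets the investigator justify not reporting a qualifying result, and Protocol 7.5 foresees patients who met withdrawal criteria but stayed in.
- **Recovery by the last visit.** Follow-up to baseline applies to items a to f, not to the ALT/AST tiers, so recovery of A and B is assumed. Protocol 4.5 and 7.2 direct end-of-treatment procedures at early discontinuation, so such a patient's last visit may fall near the crossing.
- **Categories.** SAP 8.3.5 speaks of grades, and the protocol otherwise uses that word for CTCAE. The reference to normal ranges and the Low/High rule favour three levels without settling it.
- **Scale and oversight.** The Data Monitoring Committee reviews liver elevations regularly (Protocol 7.6). Safety analysis is descriptive by design, and a hand count from about 12 patients per arm is feasible at the end.

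These points reduce the severity. They do not supply the count.

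**Conclusion.** The point holds as a minor improvement. The SAP's only categorical laboratory table describes off-drug status in completers and can score a patient who crossed a stopping limit as unchanged. No planned output states how many patients per arm met the limits in Protocol 4.4.1 or 9.4.4.

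Two stronger readings should be resisted. The interim is not blind to large rises, as shown above. Nor does the plan contradict itself: the trial-level rule in Protocol 4.4.1(g) is a pooled conduct rule and does not require a by-arm table.

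The conclusion on timing rests on values recovering by Week 20, and the conclusion on size rests on Low/Normal/High categories. The schedule table is not legible in the supplied text, so which analytes are drawn at Week 20 could not be checked beyond the safety laboratory assessment. The share of patients entering with raised ALT or AST is not given. Each patient is 8.3% of an arm of 12, or 12.5% of an assumed 8 at the interim, so the counts describe and cannot separate the doses.

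**What to change.** In SAP 8.3.5, base the categorical summary on each patient's worst on-treatment value, state the on-treatment window and the categories, and keep the last-visit shift as a supplement.

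Add one descriptive table by treatment group giving n and % meeting:

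- the three ALT/AST tiers of Protocol 4.4.1 and the composite of ALT/AST above 2x baseline with bilirubin above 2x baseline or an INR rise above 0.2 (4 rows);
- each of items a to f (6 rows);
- the confirmed eGFR limit (1 row);
- the liver event of clinical interest in Protocol 9.4.4 (1 row).

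That is 4 + 6 + 1 + 1 = 12 rows. Judge composites on results from the same draw, not on separate worst values. Use the Visit 1/Visit 2 average as baseline for liver biochemistries and INR, as SAP 5 defines it. Include Week 2 local results only where values and local ranges are in the database. Show tests per patient beside the counts. Give the same aggregate counts at the interim, which respects the rule against subject-level listings.

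The cost is some programming for strata, composites and repeat tests, on data largely already collected. Conduct and clinical limits do not change. Worst-value counts rise with the number of tests, and the small arms allow description only.

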8.3.6 ECG

A 12-lead electrocardiogram (ECG) was performed at Screening, Baseline, Week 16 and safety follow-up visit at Week 20. ECG results (normal, abnormal clinically insignificant, abnormal clinically significant) will be summarized. Listing of the patient who had gone through the ECG examination will be presented.

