8. SAFETY ANALYSIS STRATEGY

Safety analyses will be conducted using the safety analysis set on a treatment-emergent basis.

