8.3 Statistical Methods for Safety Analysis

Except otherwise stated, the analysis set for all safety analysis is the safety analysis set as defined in Section 2.2. Unless otherwise specified, all safety parameters will be summarized by treatment group by visit.

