8.3.4 Physical Examination

Physical examination results (normal/abnormal/not done) from scheduled visits will be summarized for each body system.

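### The planned ECG and physical-examination summary tables do not separate new or worsened abnormalities from pre-existing ones; baseline shift tables would.

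*SAP*

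**What the plan says.** SAP 8 opens with a general commitment: "Safety analyses will be conducted using the safety analysis set on a treatment-emergent basis". SAP 8.3 sets the default display: "Unless otherwise specified, all safety parameters will be summarized by treatment group by visit".

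Within that frame:

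- **ECG (SAP 8.3.6).** The visits are stated: "A 12-lead electrocardiogram (ECG) was performed at Screening, Baseline, Week 16 and safety follow-up visit at Week 20". The display is "ECG results (normal, abnormal clinically insignificant, abnormal clinically significant) will be summarized", followed by "Listing of the patient who had gone through the ECG examination will be presented". No change or shift from baseline is named, and the content of the listing is not described.
- **Physical examination (SAP 8.3.4).** "Physical examination results (normal/abnormal/not done) from scheduled visits will be summarized for each body system". No baseline comparison and no listing are named.
- **Vital signs (SAP 8.3.3).** Observed values and change from baseline, with a listing.
- **Laboratory values (SAP 8.3.5).** Observed values, change from baseline, a categorical shift table from baseline to the last study visit, and listings.

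Protocol 8.3.3 asks for summary statistics by treatment and visit for ECG and physical examination and adds no comparison with baseline.

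**The concern.** A count of abnormal results at a visit pools abnormalities that the patient brought into the trial with those that arose after the first dose. Equal counts at baseline and Week 16 could be read as no ECG effect when different patients are abnormal at the two visits. ECG and physical examination are both assessed before treatment (Protocol 7.2), so the information needed for a within-patient comparison is collected. They are the only repeated objective safety measures in the SAP without one, and the SAP gives no reason.

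Safety and tolerability are a listed secondary endpoint (Protocol 6.1.2, SAP 6.2). The protocol synopsis names cardiovascular events and peripheral edema among the adverse events seen with related agents, so ECG and examination findings are of some interest here.

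Physical examination has a second, smaller gap. SAP 8.3.4 confines the summary to scheduled visits. Protocol 4.4.1 provides for examinations 2-3 times per week when raised liver tests persist and close observation starts. Findings at those extra examinations fall outside the planned table.

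**Working it through.** The documents state no figure on this point, so there is nothing to reproduce. The check sets the sections side by side and then asks what by-visit counts can identify.

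**Text comparison**

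| Safety measure | By-visit summary | Comparison with own baseline | Listing |
|---|---|---|---|
| Vital signs (SAP 8.3.3) | yes | change from baseline | yes |
| Laboratory (SAP 8.3.5) | yes | change and shift table | yes |
| ECG (SAP 8.3.6) | yes, via SAP 8.3 | none named | yes, content unspecified |
| Physical examination (SAP 8.3.4) | yes, via SAP 8.3 | none named | none named |

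**What the counts identify**

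Inputs: n = 12 patients per arm (SAP 4). The number abnormal at baseline (b) and at Week 16 (f) are assumptions, because the documents give none. Both abnormal ECG categories are combined, and every patient is taken to have both assessments.

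Let a be the number abnormal at both visits. The by-visit table gives b and f but not a.

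- a lies between max(0, b + f − n) and min(b, f).
- New abnormalities = f − a, so they lie between max(0, f − b) and min(f, n − b).
- Patients at risk of a new abnormality = n − b.

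| b | f | Lowest: max(0, f − b) | Highest: min(f, 12 − b) | At risk: 12 − b | Range of proportion |
|---|---|---|---|---|---|
| 3 | 3 | 0 | min(3, 9) = 3 | 9 | 0% to 33% |
| 4 | 4 | 0 | min(4, 8) = 4 | 8 | 0% to 50% |
| 3 | 5 | 2 | min(5, 9) = 5 | 9 | 22% to 56% |
| 6 | 6 | 0 | min(6, 6) = 6 | 6 | 0% to 100% |

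For b = f = 4, the same printed table fits 0 of 8 (exact 95% interval 0% to 37%; the upper limit is 1 − 0.025^(1/8) = 0.369) and 4 of 8 (exact 95% interval 16% to 84%). A cross-tabulation against baseline supplies a and removes the ambiguity.

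**When the ambiguity arises**

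It needs at least one patient abnormal at baseline. With b = 0, every later abnormality is new and the range collapses to f. No entry criterion requires a normal ECG. Exclusion 10 covers unstable cardiovascular disease, exclusion 4 covers any history of venous thromboembolism or transient ischemic attack, and exclusion 16 lets the investigator exclude for conditions such as coronary artery disease. Abnormal baseline ECGs are therefore fewer than in an unselected group but are not ruled out.

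**The case against.** The strongest reply is that the important information reaches the report by other routes.

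- **Adverse events.** Protocol 9.4.1 requires clinically significant ECG or other examination findings to be reported as adverse events when they are detected during the study, or were present at screening and significantly worsen. Protocol 6.2.2 adds further triggers, such as accompanying symptoms or a change in dosing. SAP 8.3.2 then tabulates treatment-emergent events. This stands, and it covers the findings that matter most. It does not cover a move from normal to abnormal but not clinically significant on ECG, which is a category the SAP itself chose to report, or an examination finding that is not reported as an adverse event.
- **The ECG listing.** With 12 patients per arm and four ECG time points, a listing by visit would let a reader trace each patient. This stands in part. The content is unspecified, a listing gives no count by arm over those at risk, and no listing is named for physical examination.
- **The meaning of treatment-emergent.** SAP 8.3.2 defines the term for adverse events only: "A treatment-emergent AE is an event not present prior to exposure to investigational product or any pre-existing event that worsens following exposure to investigational product". Hence the opening sentence of SAP 8 is imprecise and cannot be read as a broken promise of a cross-tabulation for every parameter.
- **The illustration.** The upper ends for equal counts require as many patients to become normal as become abnormal (with 4 and 4, all four baseline-abnormal patients). They are arithmetical limits and say nothing about how often this would happen here.

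A reader might go further and infer that new ECG or examination abnormalities cannot be told from old ones anywhere in the report. The adverse-event route and the ECG listing rule that out. A reader might also infer that only unstable cardiac disease is excluded, or that liver-disease signs on examination are to be expected at baseline. Exclusions 4 and 16 contradict the first. The documents give no source for the second, and exclusions 3 and 6 remove ascites, encephalopathy and most raised bilirubin.

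**Conclusion.** The point holds for the summary tables. As planned, the ECG and physical-examination tables do not separate new or worsened abnormalities from pre-existing ones, and no method is given for putting these two measures on the treatment-emergent basis stated in SAP 8. The gap that remains is mainly ECG changes rated not clinically significant, and examination findings that do not become adverse events, including those found at unscheduled examinations.

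The size for this trial is unknown, because it depends on how many patients are abnormal at baseline. The ranges above rest on assumed counts and complete data in 12 patients per arm. SAP 8.2 states no formal safety hypothesis, and no primary or secondary efficacy result is affected. This is a minor improvement to descriptive outputs.

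**What to change.** Amend SAP 8.3.6 and 8.3.4 as follows, by treatment group:

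1. **ECG.** Shift tables from the last pre-dose category to Week 16 and, separately, to Week 20. Week 20 is four weeks after treatment ends and should not be pooled with Week 16.
2. **Physical examination.** For each body system, shift tables from the last pre-dose category to Week 16 and to the worst on-treatment category, including unscheduled examinations.
3. **In each table.** Give the number of patients with a new or worse category over the number at risk of it at baseline.
4. **ECG listing.** State that it shows each patient's result by visit.
5. **By-visit counts.** Keep them as supporting displays.

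Define baseline as the last pre-dose result and not simply as the Visit 3 result. Protocol 7.2 places an ECG and an examination at Visit 3, but the text available does not say whether they precede the first dose; Protocol 5.2 orders dosing only relative to blood sampling. The visit schedule tables, which are not in that text, may settle this.

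The cost is SAP wording and a few extra tables from data already collected, so a little more programming.
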